4.0 BACKGROUND & RATIONALE

4.1 Background

4.1.1 Early breast cancer

Breast cancer is the most common invasive malignancy and the most common cause of cancer-related mortality in women. The lifetime probability of developing invasive breast cancer in the United States and Europe is one in eight. Although distinct efforts have been made to optimize breast cancer treatment, up to 20-30% of early breast cancer patients will eventually develop metastases. The risk of developing distant metastases is related to the stage of disease at diagnosis and tumor biology. Hormone receptor (ER/PR) negativity is a major, poor prognostic factor. ER/PR negative breast cancer occurs most frequently in younger women, is associated with a more aggressive behavior and poorer prognosis. Although impressive efforts have been made to optimize treatment modalities in this subtype of breast cancer, the therapeutic options are still rather limited, compared to ER/PR positive breast cancer. Therefore, many researchers are still challenged by the search for new, eligible therapeutic targets.

4.1.2 Pharmaceutical and Therapeutic Background

The importance of intact immune surveillance in controlling outgrowth of neoplastic transformation has been known for decades. Accumulating evidence shows a correlation between tumor-infiltrating lymphocytes (TILs) in cancer tissue and favorable prognosis in various malignancies. In particular, the presence of CD8⁺ T-cells and the ratio of CD8⁺ effector T-cells / FoxP3⁺ regulatory T-cells seems to correlate with improved prognosis and long-term survival in many solid tumors.

The PD-1 receptor-ligand interaction is a major pathway hijacked by tumors to suppress immune control. The normal function of PD-1, expressed on the cell surface of activated T-cells under healthy conditions, is to down-modulate unwanted or excessive immune responses, including autoimmune reactions. PD-1 is an Ig superfamily member related to CD28 and CTLA-4 which has been shown to negatively regulate antigen receptor signaling upon engagement of its ligands (PD-L1 and/or PD-L2). The structure of murine PD-1 has been resolved. PD-1 and family members are type I transmembrane glycoproteins containing an Ig Variable-type (V-type) domain responsible for ligand binding and a cytoplasmic tail which is responsible for the binding of signaling molecules. The cytoplasmic tail of PD-1 contains 2 tyrosine-based signaling motifs, an immunoreceptor tyrosine-based inhibition motif (ITIM) and an immunoreceptor tyrosine-based switch motif (ITSM). Following T-cell stimulation, PD-1 recruits the tyrosine phosphatases SHP-1 and SHP-2 to the ITSM motif within its cytoplasmic tail, leading to the dephosphorylation of effector molecules such as CD3 ζ , PKC θ

and ZAP70 which are involved in the CD3 T-cell signaling cascade. PD-1 was shown to be expressed on activated lymphocytes including peripheral CD4+ and CD8+ T-cells, B-cells, Tregs and Natural Killer cells. Expression has also been shown during thymic development on CD4-CD8- (double negative) T-cells as well as subsets of macrophages and dendritic cells. The ligands for PD-1 (PD-L1 and PD-L2) are constitutively expressed or can be induced in a variety of cell types, including non-hematopoietic tissues as well as in various tumors. Both ligands are type I transmembrane receptors containing both IgV- and IgC-like domains in the extracellular region and contain short cytoplasmic regions with no known signaling motifs. Binding of either PD-1 ligand to PD-1 inhibits T-cell activation triggered through the T-cell receptor. PD-L1 is expressed at low levels on various non-hematopoietic tissues, most notably on vascular endothelium, whereas PD-L2 protein is only detectably expressed on antigen-presenting cells found in lymphoid tissue or chronic inflammatory environments. PD-L2 is thought to control immune T-cell activation in lymphoid organs, whereas PD-L1 serves to dampen unwarranted T-cell function in peripheral tissues. Although healthy organs express little (if any) PD-L1, a variety of cancers were demonstrated to express abundant levels of this T-cell inhibitor. PD-1 has been suggested to regulate tumor-specific T-cell expansion in subjects with melanoma (MEL). This suggests that the PD-1/PD-L1 pathway plays a critical role in tumor immune evasion and should be considered as an attractive target for therapeutic intervention.

Pembrolizumab is a potent and highly selective humanized monoclonal antibody (mAb) of the IgG4/kappa isotype designed to directly block the interaction between PD-1 and its ligands, PD-L1 and PD-L2. Keytruda® has been approved in Belgium for inoperable or metastatic melanoma and non-small lung cancer.

4.1.3 Biomarkers to predict and monitor response to pembrolizumab (Keytruda®)

As only a subset of patients treated with immune checkpoint antibodies experience durable and long-term disease control, predictive biomarker development has become a top priority. Tumor PD-L1 expression has been pursued as a potential biomarker and studies have demonstrated that PD-L1 baseline expression level showed strong association with response to anti-PD-1 therapy. However, clinical responses were observed also in patients considered to be negative for PD-L1 expression in the tumor. However, the appearance of measurable anti-tumor activity may take longer for immune therapies than for cytotoxic therapies and lesions may enlarge before shrinking. Therefore, identification of biomarkers to monitor early response are urgently needed.

4.1.4 Preclinical and Clinical Trial Data

We refer to the Investigator's Brochure for Preclinical and Clinical data.

4.2 Rationale

4.2.1 Rationale for the Trial and Selected Subject Population

There is an urgent need for new treatment strategies in patients with ER/PR negative breast cancer. Different clinical studies with anti-PD-1 therapy show clear evidence of clinical benefit in terms of overall survival, demonstrating immune modulating of ICPs as a promising new

targeted therapy in different types of cancer, even in less immune-driven subtypes of cancer. However, most of these studies are performed in metastatic stages of malignant melanoma, non-small cell lung cancer etc. No studies are available on the response to immune therapy in early stages of cancer. In addition, data on ICPs-expression and the effect of ICP- inhibition therapy (e.g. PD-1 inhibition) are rather scarce in breast cancer, as well as criteria to evaluate response in early stage of disease. Investigation of potential biomarkers is urgently needed to identify the subgroup of patients that will benefit from immunotherapy. This will optimize the therapeutic efficacy, prevent toxicity and reduce the costs associated with immunotherapy.

Tumor cells show increased response to immunotherapy after they became more immunogenic by therapy-induced immunogenic cell death (ICD) e.g. chemotherapy, radiotherapy etc. This process might be of special interest/benefit in less immunogenic-driven tumors. BC has traditionally not been considered as a highly immunogenic neoplasm, but there is increasing evidence for dynamic cross-talk between the host-immune system and BC cells. In addition, certain subgroups of BC (mainly ER/PR negative tumors) display presence of a massive lymphocytic tumor-infiltrate (TILs), which have been shown to be a potential key factor in the response to immunomodulatory therapy. Therefore, anthracycline based chemotherapy, followed by immunotherapy (e.g. PD-1 inhibition therapy) might be promising in BC.

There are currently little data regarding efficacy of immunotherapy in ER+ breast cancers. This subtype is generally considered to be less immunogenic than ER/PR negative breast cancer. The relationship in ER+ breast cancer is more complicated due to the association of TILs with higher proliferation rates, with the latter being associated with poorer outcomes in luminal breast cancers. However, immunotherapy could be an option for patients in with ER+ breast cancer with a high amount of TILs.

This phase 0 study allows short-term evaluation of the effect of anti-PD1 therapy in early breast cancer with biomarker determination by comparing histological markers pre-treatment and at surgery.

Changes in biomarkers related to intratumoral immunity and proliferation may provide evidence for biological activity of pembrolizumab (Keytruda®) and may allow the development of a blood-based biomarker to help predict which patients may benefit from Pembrolizumab (Keytruda®) and to monitor therapy response.

To evaluate whether neo-adjuvant chemotherapy can alter expression of biomarkers related to intratumoral immunity and proliferation, patients will also be enquired to provide a new core biopsy after the last dose of chemotherapy.

4.2.2 Rationale for Dose Selection/Regimen/Modification

An open-label Phase 1 trial (Protocol 001) is being conducted to evaluate the safety and clinical activity of single agent MK-3475. The dose escalation portion of this trial evaluated three dose levels, 1 mg/kg, 3 mg/kg, and 10 mg/kg, administered every 2 weeks (Q2W) in

subjects with advanced solid tumors. All three dose levels were well tolerated and no dose-limiting toxicities were observed. This first in human study of MK-3475 showed evidence of target engagement and objective evidence of tumor size reduction at all dose levels (1 mg/kg, 3 mg/kg and 10 mg/kg Q2W). No MTD has been identified to date. 10.0 mg/kg Q2W, the highest dose tested in PN001, will be the dose and schedule utilized in Cohorts A, B, C and D of this protocol to test for initial tumor activity. Recent data from other clinical studies within the MK-3475 program has shown that a lower dose of MK-3475 and a less frequent schedule may be sufficient for target engagement and clinical activity.

PK data analysis of MK-3475 administered Q2W and Q3W showed slow systemic clearance, limited volume of distribution, and a long half-life (refer to IB). Pharmacodynamic data (IL-2 release assay) suggested that peripheral target engagement is durable (>21 days). This early PK and pharmacodynamic data provides scientific rationale for testing a Q2W and Q3W dosing schedule.

A population pharmacokinetic analysis has been performed using serum concentration time data from 476 patients. Within the resulting population PK model, clearance and volume parameters of MK-3475 were found to be dependent on body weight. The relationship between clearance and body weight, with an allometric exponent of 0.59, is within the range observed for other antibodies and would support both body weight normalized dosing or a fixed dose across all body weights. MK-3475 has been found to have a wide therapeutic range based on the melanoma indication. The differences in exposure for a 200 mg fixed dose regimen relative to a 2 mg/kg Q3W body weight based regimen are anticipated to remain well within the established exposure margins of 0.5 – 5.0 for MK-3475 in the melanoma indication. The exposure margins are based on the notion of similar efficacy and safety in melanoma at 10 mg/kg Q3W vs. the proposed dose regimen of 2 mg/kg Q3W (i.e. 5-fold higher dose and exposure). The population PK evaluation revealed that there was no significant impact of tumor burden on exposure. In addition, exposure was similar between the NSCLC and melanoma indications. Therefore, there are no anticipated changes in exposure between different indication settings.

The rationale for further exploration of 2 mg/kg and comparable doses of pembrolizumab in solid tumors is based on: 1) similar efficacy and safety of pembrolizumab when dosed at either 2 mg/kg or 10 mg/kg Q3W in melanoma patients, 2) the flat exposure-response relationships of pembrolizumab for both efficacy and safety in the dose ranges of 2 mg/kg Q3W to 10 mg/kg Q3W, 3) the lack of effect of tumor burden or indication on distribution behavior of pembrolizumab (as assessed by the population PK model) and 4) the assumption that the dynamics of pembrolizumab target engagement will not vary meaningfully with tumor type.

The choice of the 200 mg Q3W as an appropriate dose for the switch to fixed dosing is based on simulations performed using the population PK model of pembrolizumab showing that the fixed dose of 200 mg every 3 weeks will provide exposures that 1) are optimally consistent with those obtained with the 2 mg/kg dose every 3 weeks, 2) will maintain individual patient exposures in the exposure range established in melanoma as associated with maximal efficacy response and 3) will maintain individual patients exposure in the exposure range established in melanoma that are well tolerated and safe.

A fixed dose regimen will simplify the dosing regimen to be more convenient for physicians and to reduce potential for dosing errors. A fixed dosing scheme will also reduce complexity in the logistical chain at treatment facilities and reduce wastage.

4.2.3 Rationale for Endpoints

4.2.3.1 Biomarker Research

PD-L1: Previous studies have shown a correlation between PD-L1 expression and an objective response in patients treated with anti-PD-1/L1 therapy. However this finding is not consistent among all studies. It also raises the question whether clinical decisions regarding the treatment of patients who have failed conventional therapies and for whom no other treatments are available should be based on PD-L1 expression. On the basis of these controversial results, we will evaluate the potential predictive role of PD-L1 expression in tumor cells.

TILs: TILs might be the primary predictors of response to ICP therapy. Tumors with a large amount of TILs are more likely to respond to anti PD-1/L1 therapy.

Ki67: Immunohistochemical assessment of the proportion of cells staining for the nuclear antigen Ki67 has become the most widely used method for comparing proliferation between tumor samples. In spite of consistent data on Ki67 as a prognostic marker in early breast cancer, its role in breast cancer management remains uncertain. Reductions in Ki67 occur in the tumors of most patients receiving systemic treatment, and there is some evidence that there are greater reductions in patients who respond to treatment.

Except from the above mentioned biomarkers will blood and tissue samples be used to study other possible biomarkers and T-cell subpopulations. These tests will be performed in cooperation with KU Leuven laboratories.

5.0 METHODOLOGY

5.1 Entry Criteria

5.1.1 Diagnosis/Condition for Entry into the Trial

For the retrospective study (S58910)

All breast cancer patients diagnosed and treated at the Leuven Multidisciplinary Breast Center (University Hospitals Leuven) are documented in a clinical-pathological database, containing extensive general and tumor-related information, as well as clinical follow-up such as relapse and cause of death. This database contains data from over 10000 patients and is linked to a tumor and blood bank. For the proposed study patients will be selected from this database based on the following criteria:

- Diagnosed between 2005 and 2010 with non-metastatic primary invasive breast cancer
- Primary surgery in our institution
- Treated with upfront surgery
- ER/PR negative breast cancer (Allred score)
- Primary tumor >2cm
- Stratification for Her2 status evaluated using IHC followed by FISH

For the prospective Phase 0 study

Patients must meet all of the following criteria to be eligible for study entry:

- Non-metastatic newly diagnosed primary invasive carcinoma of the breast
- Primary tumor > 1 cm
- Negative estrogen (ER) and progesterone (PR) receptor status OR
Positive estrogen receptor (ER) status with TIL expression on core biopsy

5.1.2 Subject Inclusion Criteria

In order to be eligible for participation in this trial, the subject must:

1. Be willing and able to provide written informed consent/assent for the trial.
2. Be ≥ 18 years of age on day of signing informed consent.
3. Be willing to provide tissue from a newly obtained core or excisional biopsy of a tumor lesion if needed. *Newly obtained is defined as a specimen obtained up to 6 weeks (42 days) prior to initiation of treatment on Day 0. Subjects for whom newly obtained samples cannot be provided (e.g. inaccessible or subject safety concern) may submit an archived specimen only upon agreement from the Sponsor.*
4. Have a performance status of 0 or 1 on the ECOG Performance Scale.
5. Have non-metastatic operable newly diagnosed primary invasive carcinoma of the breast that is:
 - a. Histologically confirmed
 - b. ER/PR negative or ER positive breast cancer with TIL expression on core biopsy. ER/PR status will be evaluated with Allred score (semi-quantitative measurement) following ASCO CAP guidelines 2009. TIL count based on the guidelines of the International TILS Working Group on Breast Cancer
 - c. HER2 negative or positive. HER2 status will be evaluated using IHC followed by FISH with dual probe (ASCO CAP guidelines 2013).

- d. Primary tumor size greater than 1 cm, measured by any of clinical examination, mammography, ultrasound or magnetic resonance imaging
 - e. Any clinical nodal status
6. Have evaluable core biopsy for IHC
 7. Be willing to provide plasma/blood samples
 8. After neo-adjuvant chemotherapy (cohort B1 and B2) patients must have residual tumor >1cm and must be willing to provide evaluable new tumor biopsy for IHC
 9. Demonstrate adequate organ function as defined in Table 1, all screening labs should be performed within 14 days of treatment initiation.

Table 1 Adequate Organ Function Laboratory Values

System	Laboratory Value
Hematological	
Absolute neutrophil count (ANC)	≥1,500 /mcL
Platelets	≥100,000 / mcL
Hemoglobin	≥9 g/dL or ≥5.6 mmol/L without transfusion or EPO dependency (within 7 days of assessment)
Renal	
Serum creatinine OR Measured or calculated ^a creatinine clearance (GFR can also be used in place of creatinine or CrCl)	≤1.5 X upper limit of normal (ULN) OR ≥60 mL/min for subject with creatinine levels > 1.5 X institutional ULN
Hepatic	
Serum total bilirubin	≤ 1.5 X ULN OR Direct bilirubin ≤ ULN for subjects with total bilirubin levels > 1.5 ULN
AST (SGOT) and ALT (SGPT)	≤ 2.5 X ULN OR ≤ 5 X ULN for subjects with liver metastases
Albumin	≥2.5 mg/dL
Coagulation	
International Normalized Ratio (INR) or Prothrombin Time (PT)	≤1.5 X ULN unless subject is receiving anticoagulant therapy as long as PT or PTT is within therapeutic range of intended use of anticoagulants
Activated Partial Thromboplastin Time (aPTT)	≤1.5 X ULN unless subject is receiving anticoagulant therapy as long as PT or PTT is within therapeutic range of intended use of anticoagulants
^a Creatinine clearance should be calculated per institutional standard.	

10. Female subject of childbearing potential should have a negative urine or serum pregnancy test within 72 hours prior to receiving the study medication. If the urine test is positive or cannot be confirmed as negative, a serum pregnancy test will be required.
11. Female subjects of childbearing potential (Section 5.7.2) must be willing to use an adequate method of contraception as outlined in Section 5.7.2 – Contraception, for the course of the study through 120 days after receiving the study medication.

Note: Abstinence is acceptable if this is the usual lifestyle and preferred contraception for the subject.

12. Male subjects of childbearing potential (Section 5.7.1) must agree to use an adequate method of contraception as outlined in Section 5.7.1- Contraception, until 120 after receiving the study therapy.

Note: Abstinence is acceptable if this is the usual lifestyle and preferred contraception for the subject.

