 - For **Grade 3 or 4 diarrhea/colitis**, treat with intravenous steroids followed by high dose oral steroids.
 - When symptoms improve to Grade 1 or less, steroid taper should be started and continued over no less than 4 weeks.
- **Type 1 diabetes mellitus (if new onset, including diabetic ketoacidosis [DKA]) or \geq Grade 3 Hyperglycemia, if associated with ketosis (ketonuria) or metabolic acidosis (DKA)**
 - For **T1DM** or **Grade 3-4 Hyperglycemia**
 - Insulin replacement therapy is recommended for Type I diabetes mellitus and for Grade 3-4 hyperglycemia associated with metabolic acidosis or ketonuria.
 - Evaluate patients with serum glucose and a metabolic panel, urine ketones, glycosylated hemoglobin, and C-peptide.
- **Hypophysitis:**
 - For **Grade 2** events, treat with corticosteroids. When symptoms improve to Grade 1 or less, steroid taper should be started and continued over no less than 4 weeks. Replacement of appropriate hormones may be required as the steroid dose is tapered.
 - For **Grade 3-4** events, treat with an initial dose of IV corticosteroids followed by oral corticosteroids. When symptoms improve to Grade 1 or less, steroid taper should be started and continued over no less than 4 weeks. Replacement of appropriate hormones may be required as the steroid dose is tapered.
- **Hyperthyroidism or Hypothyroidism:**

Thyroid disorders can occur at any time during treatment. Monitor patients for changes in thyroid function (at the start of treatment, periodically during treatment, and as indicated based on clinical evaluation) and for clinical signs and symptoms of thyroid disorders.

- **Grade 2** hyperthyroidism events (and **Grade 2-4** hypothyroidism):
 - In hyperthyroidism, non-selective beta-blockers (e.g. propranolol) are suggested as initial therapy.
 - In hypothyroidism, thyroid hormone replacement therapy, with levothyroxine or liothyronine, is indicated per standard of care.
- **Grade 3-4** hyperthyroidism
 - Treat with an initial dose of IV corticosteroid followed by oral corticosteroids. When symptoms improve to Grade 1 or less, steroid taper should be started and continued over no less than 4 weeks. Replacement of appropriate hormones may be required as the steroid dose is tapered.
- **Hepatic:**
 - For **Grade 2** events, monitor liver function tests more frequently until returned to baseline values (consider weekly).
 - Treat with IV or oral corticosteroids

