6.0 TRIAL FLOW CHART

Study Flow Chart

Trial period	Screening	Administration	Surgery	Post-op
Scheduling window (days)	-14 to 0	0	10 +/-4	30+/-7
Administrative procedures				
Informed consent	x			
Inclusion/exclusion criteria	x			
Demographics and medical history	x			
Prior and concomittant medication review	x	x	x	x
Labo processing/assesment (local)				
Pregnancy test	x			
CBC with differentiation	x		x	x
Chemistry	x		x	x
TSH, (T3, FT4)	x			x
Urinalysis	x		x	x
Labo (central)				
Blood sample	x		x	x
Tumor tissue collection				
Newly/archival tissue collection	x*		x	
Clinical procedures/assesments				
Review adverse events	x		x	x
ECG	x			
Physical examination	x	x	x	x
Vital signs, weight, height	x	x	x	x
ECOG performance status	x			
Pembrolizumab administration		x		
Anti-cancer therapy status				x
Survival status				x

* Only necessary for cohort B, but will be collected as well in cohort A for further research requiring fresh material, in case patients of cohort A are willing to provide a new fresh tumor sample (with biopsy).

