7.1.3 Laboratory Procedures/Assessments

Details regarding specific laboratory procedures/assessments to be performed in this trial are provided below Laboratory Safety Evaluations (Hematology, Chemistry and Urinalysis)

Laboratory tests for hematology, chemistry, urinalysis, and others are specified in Table 5.

Table 5 Laboratory Tests

Hematology	Chemistry	Urinalysis	Other
Hematocrit	Alkaline phosphatase	Test strip screening:	Serum β -human chorionic gonadotropin†
Hemoglobin	Alanine aminotransferase (ALT)	Glucose	(β -hCG)†
Platelet count	Aspartate aminotransferase (AST)	Ketons	PT (INR)
WBC (total and differential)	Lactate dehydrogenase (LDH)	Specific gravity	aPTT
Red Blood Cell Count	Biocarbonate	Heam	Total thriiodothyronine (T3)
Absolute Neutrophil Count	Ureum	pH	Free tyroxine (T4)
Absolute Lymphocyte Count	Total Calcium	Protein	Thyroid stimulating hormone (TSH)
	Creatinine	Nitrite	
	Chloride	Leuco-esterase	
	Phosphate	Bilirubine	Blood for correlative studies
	Potassium	Urobilinogeen	
	Sodium		
	Gamma GT	Urine pregnancy test †	
	Total Bilirubin		
	Direct Bilirubin (If total bilirubin is elevated above the upper limit of normal)		
	Total protein		

† Perform on women of childbearing potential only. If urine pregnancy results cannot be confirmed as negative, a serum pregnancy test will be required.

‡ If considered standard of care in your region.

Laboratory tests for screening or entry into the Second Course Phase should be performed within 14 days prior to the first dose of treatment. After Cycle 1, pre-dose laboratory procedures can be conducted up to 72 hours prior to dosing. Results must be reviewed by the investigator or qualified designee and found to be acceptable prior to each dose of trial treatment.

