7.1.5.1 Screening

7.1.5.1.1 Patients with ER/PR negative OR ER positive with TILs on core biopsy, and residual tumour of at least 1 cm after neo-adjuvant chemotherapy will be screened before surgery as well as patients with ER/PR negative breast cancer only scheduled for surgery and adjuvant therapy if applicable. Screening Period

Patients will be screened at a maximum of 14 days before administration of Pembrolizumab.

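### The albumin eligibility limit in Table 1 is printed in mg/dL, where it would exclude nobody if g/dL was meant, and albumin is in neither Table 5 nor the flow chart

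*Combined protocol and SAP*

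**What the plan says.** **Albumin.** Table 1 (Section 5.1.2, criterion 9) sets a lower limit of 2.5 mg/dL. Hemoglobin, in the same table, is given in g/dL. Criterion 9 adds that "all screening labs should be performed within 14 days of treatment initiation". Section 7.1.3 refers to Table 5 for the laboratory tests. The Table 5 chemistry column includes total protein but not albumin. The flow charts (Sections 2.2 and 6.0) have a general chemistry row and do not name albumin.

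**Pregnancy test.** Criterion 10 reads: "Female subject of childbearing potential should have a negative urine or serum pregnancy test within 72 hours prior to receiving the study medication". Both flow charts have one row, "Pregnancy test", marked under Screening (day -14 to 0) and not under Administration. Section 7.1.5.1 states: "Patients will be screened at a maximum of 14 days before administration of Pembrolizumab". Section 7.1.3 states: "Laboratory tests for screening or entry into the Second Course Phase should be performed within 14 days prior to the first dose of treatment". The Table 5 footnote on the pregnancy test gives no timing; it says "If urine pregnancy results cannot be confirmed as negative, a serum pregnancy test will be required".

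**Coagulation.** Table 1 limits INR or PT, and aPTT, to 1.5 times the upper limit of normal, with an exception for anticoagulated patients. Table 5 lists PT (INR) and aPTT under Other. Neither flow chart has a coagulation row.

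**Glucose.** Section 5.4.1 covers new-onset type 1 diabetes and Grade 3 or higher hyperglycemia when it comes with ketosis or metabolic acidosis. It instructs: "Evaluate patients with serum glucose and a metabolic panel, urine ketones, glycosylated hemoglobin, and C-peptide". Table 5 has glucose only on the urine test strip.

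**The concern.** An eligibility limit works only if the number is right and the test is on the list that sites order from. Albumin is in doubt on both counts. The printed unit makes the limit one that no patient could fail, and the laboratory list does not ask for the measurement. A site could order exactly what Table 5 specifies and have no albumin result to check. A site that has a result and applies the limit as printed would exclude nobody. Table 1 applies to all six cohorts, and these patients have surgery 10 ± 4 days, that is 6 to 14 days, after dosing.

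The pregnancy and coagulation items are related but weaker. The requirement exists in each case, and the flow chart does not display it in full. The risk is a protocol deviation at a site that works from the grid alone.

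**Working it through.** There is no power, alpha or sample-size figure to reproduce. The check sets each eligibility requirement beside the sections that schedule it.

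**1. Albumin unit.**
- Input: the printed limit of 2.5 mg/dL (Table 1).
- Assumption: serum albumin is measured in g/dL and the intended limit was 2.5 g/dL. The documents do not say so; the only pointer is that hemoglobin in the same table is in g/dL.
- Conversion: 1 g/dL = 1,000 mg/dL, so the presumed limit is 2.5 × 1,000 = 2,500 mg/dL.
- Ratio of presumed to printed limit: 2,500 / 2.5 = 1,000.
- An albumin of x g/dL fails the printed limit only if 1,000x < 2.5, that is x < 0.0025 g/dL. On the assumption, no patient has such a value, so the limit excludes nobody.

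**2. Coverage of the disputed Table 1 tests.**

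| Table 1 test | In Table 5 | Named in a flow-chart row | Time limit |
|---|---|---|---|
| Albumin | No (total protein only) | No | 14 days, criterion 9 |
| INR/PT | Yes, under Other | No | 14 days, criterion 9 and Section 7.1.3 |
| aPTT | Yes, under Other | No | 14 days, criterion 9 and Section 7.1.3 |

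Albumin is the only one of the three that is in no laboratory list. The coagulation tests are specified and have a time limit; they lack only a flow-chart row. Table 5 assigns no visit to any analyte, so the absence of a visit there does not single them out. One Table 5 footnote, about regional standard of care, has no visible anchor in the available text and cannot be tied to these tests.

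**3. Pregnancy-test window.**
- Schedule: up to 14 days, or 14 × 24 = 336 hours. Criterion 10: 72 hours, or 3 days.
- In whole calendar days, day -14 to day 0 is 15 days. Days -3 to 0 (4 days) meet criterion 10, and 15 - 4 = 11 days (day -14 to -4) do not.
- A test on days -3 to 0 satisfies both texts. The shorter window lies inside the longer one, so they do not contradict each other.
- The only 72-hour wording in Section 7.1.3 applies after Cycle 1, and this single-dose trial has no later cycle.

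**4. Glucose.** Urinalysis is scheduled at Screening, Surgery and Post-op, and the strip covers glucose and ketones. The chemistry list includes bicarbonate but not serum glucose.

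**The case against.** The strongest reply is that every requirement is already binding. Section 7.1 says the flow chart summarizes the procedures, and Section 7.1.1.2 has the investigator or designee review all eligibility criteria. Criterion 9 with Table 1 therefore still demands an albumin result within 14 days of treatment. The mg/dL is probably a misprint that a site would read correctly.

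Much of that stands. It does not remove the albumin point. Table 5 is the stated specification of the tests and omits an eligibility analyte, and an eligibility threshold should not depend on sites silently correcting the unit.

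The same reply defeats three stronger readings that a reader might infer:

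- *The protocol permits dosing on a pregnancy test up to 14 days old.* It does not. Criterion 10 forbids it, exclusion 13 separately bars pregnant patients, and Section 7.1.3 requires laboratory results to be reviewed and acceptable before dosing. Section 5.2.4 does tie dosing to completion of the flow-chart procedures, so a site that looks only at the grid could slip. That is a deviation risk, and the 11 of 15 days describes the window, not how many women would be affected.
- *Clotting is not scheduled before surgery.* PT (INR) and aPTT are in Table 5 and fall under the 14-day screening rule.
- *Hyperglycemia would go unmonitored.* Section 5.4.1 acts on hyperglycemia with ketosis or acidosis, the scheduled urine strip looks for glucose and ketones, serum glucose is ordered once the event is suspected, and Section 7.1 allows unscheduled tests. Glucose is also not an eligibility test.

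**Conclusion.** The point holds for albumin. As printed, the Table 1 limit is lower by a factor of 1,000 than the presumed one and excludes nobody. This rests on the assumption that serum albumin is measured, and the limit was meant, in g/dL. If mg/dL was truly intended, the unit finding falls away and only the omission remains. The omission of albumin from Table 5 and from both flow charts is a matter of text and needs no assumption.

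The pregnancy-test window and the coagulation row are clarifications only, since both requirements are already in force. Serum glucose is an optional improvement.

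The documents do not support calling this a general failure of safety screening. The consequence is eligibility conduct, with no effect on the biomarker endpoints, the analysis or the target of 54 patients.

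**What to change.** **Needed**
- Check the albumin unit in Table 1 and correct it, to g/dL if that was meant.
- Add albumin to the Table 5 chemistry list. The cost is one more analyte on a tube already drawn. The chemistry row covers Screening, Surgery and Post-op, so mark albumin as Screening only if it serves eligibility alone.

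**Clarifications**
- Footnote the pregnancy-test row in both flow charts with the 72-hour limit of criterion 10, and exempt that test from the 14-day statement under Table 5. Women screened early may need a repeat urine test, which criterion 10 already implies.
- Add a Screening row for PT (INR) and aPTT to both flow charts. The tests are already required, so this is wording only.

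**Optional**
- Add serum glucose to the same chemistry panel, because the scheduled visits measure glucose only by urine strip. This is a second analyte on the same tube.
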